## 2. Reporting procedures for serious adverse events or reactions

Any adverse event (AE) occurring to a participant will be reported to the MS IDREC. Reports of related (resulted from administration of any of the research procedures) and unexpected (the type of event is not listed in the protocol as an expected occurrence) adverse events will be reported as soon as possible once the Principal Investigator becomes aware of the event. Unrelated/expected adverse events will be reported within 10 working days of the Principal Investigator becoming aware of the event.

All SUSARs will be reported to the MHRA in addition to the MS IDREC. For fatal and life-threatening SUSARs, this will be reported as soon as possible, but no later than 7 calendar days after the PI is first aware of the reaction. Any additional relevant information will be reported within 8 calendar days of the initial report. Non-fatal or non-life-threatening SUSARs will also be reported as soon as possible, and no later than 15 days after the PI is first aware of the reaction.

All reports to the MHRA will be via the [Yellow Card Scheme](#).

## 3. Safety of participants

### 1. What level of baseline safety screening will take place for this research?

All participants will undergo a two screening visits (one online; one in-person in the Department of Psychiatry) to ensure only eligible participants take part. The following will be recorded at baseline screening:

- Demographic data, including age (years and months), years in full time education, gender
- Medical history review, details of current and past medication
- SCID-V Interviews (Structured clinical Interview for DSM-V, a set of standard clinical questions asking about current and past psychiatric illness)
- Weight, height measurement
- Vital signs assessment (blood pressure, heart rate)

- 12 lead ECG (to check for heart electrical abnormalities)
- Urine drug screening
- Urine pregnancy test (females only)
- MRI Safety questionnaire

**2. Provide details about the safety monitoring of participants and the staff/researchers carrying this out**

On the study visit, where the participant will either take a single dose of pitolisant or placebo, participants will be advised to have not consumed alcohol within the past 24 hours. Participants will be asked to arrive via walking or public transport or taxi, and will be asked to continue to avoid driving, operating heavy machinery or using a bicycle for at least the following 12 hours (maximum half-life of pitolisant). All participants will receive a phone number for calling an out-of-hours BRC on-call medic service in case they need medical advice related to the study after the study visit has taken place.

The randomisation code will be broken if a participant requires treatment for a new medical condition/experiences serious adverse reactions and either of these situations make it clinically important to know what medication they are taking. In order to unblind the participant, the study medic/delegated medic will have access to the randomisation code and can unblind if necessary within a maximum of 1 hour. If breaking the code is necessary then only that individual's code will be broken. Data from unblinded participants will not be admitted to analysis. If unblinding occurs, the researcher will record the reason and result of the unblinding, as well as the date and time of the event.

**3. Give details on the medical cover required and who will provide this cover**

A medical doctor who is part of the research team will review the screening and make a final judgment about including participants in the study. A qualified medical doctor will be contacted if a participant expresses concern to a named researcher regarding side effects or health status changes during the study week.

**4. Will the participants' GP be informed about their participation in the research? In not, please justify**

Participants' GPs will not be informed about their participation in the study. A single dose of pitolisant is not regarded as a clinically significant intervention and is not expected to have any impact on participants' health or wellbeing. We are excluding participants who are pregnant, breastfeeding or who have any medical conditions for whom the study would not be suitable.

**5. What is your planned procedure if an incidental finding is suspected?**

Participants will be screened to exclude those with past or current serious psychiatric illness and Best Practice Guidance (BPG) 08 (Psychological distress) will be followed in order to ensure best practice in situations where participants with psychological distress are identified. The guidance in this document around confidentiality and researcher training will also be adhered to.

Incidental findings from MRI investigations at WIN facilities will be treated in accordance with the Incidental Findings SOP (APPENDIX I - INCIDENTAL FINDINGS FOR NEUROIMAGING RESEARCH SOP).

Urine pregnancy and drug screens: participants will be explicitly informed that their urine samples will be tested for pregnancy and recreational drug use, both in the pre-screening telephone call and during the Screening Visit, and informed of their right to withdraw from the study. They will also be told in advance that if the drug screen returns positive results, they will be excluded from the study. If participants consent to providing a urine sample for the pregnancy test and the test result is positive, the researcher will act in accordance with the pregnancy urine test SOP (APPENDIX O - URINE PREGNACY TEST SOP), wherein they will feed the result back to the medic covering the visit or a member of the research team, before communicating the result to the participant and providing any relevant advice. Results of the screening will remain confidential within the study team and participants will be informed of this.

**6. If an incidental finding has clinical implications, what action will you take?**

If a researcher has concerns that a volunteer may have an undiagnosed psychiatric condition that is causing distress (identified during the screening visit or following review of the mood-related questionnaires), CUREC

guidance (BPG08) will be followed. The researcher will seek advice from the Principal Investigator who may discuss the symptoms in greater detail with the volunteer and/or offer the opportunity to speak with a senior clinical researcher. If the volunteer indicates that they are not currently receiving support and it is felt necessary, they will be encouraged to contact their General Practitioner.

#### 4. Ethical considerations

Research usually carries the risk of some ethical challenge. If this is the case you need to demonstrate your awareness of the problem and your response to mitigate ethical objections.

For guidance on ethical issues, please see <http://researchsupport.admin.ox.ac.uk/governance/ethics/resources>, however the following areas are often a cause for concern:

1. Will the research involve any participants considered vulnerable in the context of the research (e.g. children, elderly, prisoners, adults at risk)?
 
If yes, please describe how they are defined as vulnerable and detail any CUREC Approved Procedures or guidance that will be applied to the research (for current documents and templates see https://researchsupport.admin.ox.ac.uk/governance/ethics/resources).
	Yes 	No 
---	------------------------------	--

2. Will the research involve deliberate deception of participants?
 
If yes, justify why deception is used, describe deception and debriefing process, and include debriefing documents in the application
	Yes 	No 
--	------------------------------	--

3. Could the proposed research affect your own physical and/or psychological safety as a researcher?
 
If yes, describe how this will be mitigated.
	Yes 	No 
---	------------------------------	--

4. Does your research raise issues relevant to the Counter-Terrorism and Security Act (the Prevent Duty), which seeks to prevent people from being drawn into terrorism?
 
If yes, please say how you plan to address any related risks. Please see advice on this on our Best Practice Guidance Web Page.
	Yes 	No 
--	------------------------------	--

**5. Please list any stakeholder or community engagement that has been, or will be, undertaken in relation to the research**

Prior to this research study, we engaged in a public and patient involvement project to learn more about the experiences of cognitive impairment in persons with lived experience of depression. This project highlighted the many consequences of cognitive impairment to clinical engagement and quality of life, as well as the desire for therapeutics to be developed which may address these issues. Full details of this project will be published in an article ([name] *et al.*, in review), or can be accessed upon request.

**6. Please give details of any other research-specific ethical and/or safety considerations, not related to drug/substance administration**

During the MRI procedure, there is a small risk that participants feel some degree of discomfort given the enclosed space of the scanner. Discomfort from lying still for a long period of time will be minimised with comfortable padding and positioning. Whilst in the scanner, participants will be able to use the alarm if they wish to communicate with the operator or to interrupt scanning. People with a history of severe claustrophobia would be excluded from participation in the study. All participants will be introduced carefully to the scanner and informed that they can terminate the scan session at any stage, should they wish to do so. Once inside the scanner, participants will be able to indicate if they wish the scanning to cease by squeezing a bulb placed in their hand, or by requesting verbally. As the MRI scanner is noisy, participants will be given earplugs to minimise the noise.

MRI is a safe, non-invasive technique, which does not involve ionising radiation. Risks associated with the magnetic field will be removed by excluding potential participants with ferromagnetic objects in their bodies (e.g., metal implants, vessel clips, shrapnel injuries) or with implanted devices, which may be damaged by the magnet (e.g., heart pacemakers). All people entering the scanning room are screened for such objects. All people will complete an MRI Screening safety questionnaire before taking part in the study. In the instance of incidental findings emerging from neuroimaging data, study researchers will follow the relevant incidental findings SOP (APPENDIX I - INCIDENTAL FINDINGS FOR NEUROIMAGING RESEARCH SOP). Researchers helping during the MRI scanning process will undertake complete magnet safety training and an in-person building induction at WIN facilities to ensure maximal awareness and safety around the scanner and for each research volunteer.

**7. Will any data or information from this study be provided to individual participants?**

N/A

**Section J. Statistics and analysis**

**1. Do you have a statistical plan?**

Yes  No

If no, please justify.

N/A

**2. Number of Participants**

56 healthy volunteers (28 per group)

**3. Have you done a sample size calculation?**

Yes  No

If yes, please give details below

If no, please give details to indicate you have considered the implications the selected sample size will have on the research outcome

The selected sample size was informed by a priori statistical power analysis (APPENDIX P – POWER CALCULATION READ-OUT) for a one-way fixed effects ANOVA approach within a healthy volunteer population via G\*Power Software (Statistical power: 80%; Estimated effect size: 0.4; Alpha level: 0.05), which requires a total sample size of 52 to power (an additional 4 persons will be recruited in case of data quality issues and/or drop-out). The sample size calculation is conservative and informed by a previous placebo-controlled cross-over study of cognitive function in healthy volunteers (N=16) following a short course of an histamine-1 agonist/histamine-3 antagonist (betahistine). The study demonstrated large between-group differences in n-back accuracy ( $\eta_p^2 = 0.74$ ) and BOLD activation within the Inferior frontal gyrus and medial temporal gyrus during the n-back task ( $\eta_p^2 = 0.78$  and  $\eta_p^2 = 0.79$ , respectively).

#### 4. Analysis of Outcome Measures

R Software will be used to analyse all psychometric, cognitive and neuroimaging data. Sample characteristic data (e.g. age, gender, and years in education) will be analysed using an appropriate analysis of variance (e.g. t-test or Mann-Whitney U), depending on model assumptions being satisfied. Cognitive and neuroimaging data will be analysed using a between-groups ANOVA approach, with appropriate normality transformations and Greenhouse–Geisser correct where the distribution and/or degrees of freedom does not meet model assumptions. Post-hoc analyses will be corrected using Bonferroni (or Bonferroni-Holm) correction. Analysis of fMRI endpoints will be completed using the FSL software package.

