### **Screening visit:**

Participants who met the eligibility criteria during the online screening then would be invited to book themselves into a screening visit occurring at the Neurosciences Building, Warneford Hospital Site. The visit will take approximately 60-90 minutes to complete. A physical copy of informed consent will be taken at the start of visit as the consent obtained during the online screening would have been done remotely. The screening visit involves the following procedures:

- Personal contact details collection (paper)
- Weight, height measurement
- Vital signs assessment (blood pressure and ECG to check for heart electrical abnormalities)
- 12 lead ECG
- Urine drug screening
- Urine pregnancy test
- Digital Span Task – Forward/Backwards (to assess baseline cognitive ability for randomisation procedure); this task will require participants to repeat a sequence of numbers in a particular order (forwards or backwards) orally to the researcher.
- SCID-V Interview (Structured clinical Interview for DSM-V, a set of standard clinical questions asking about current and past psychiatric illness)
- MRI screening form

All physical health assessments will be overseen by the medical officer attached to this study ([name]) or other delegated medical professional. For the ECG assessment, a chaperone will be offered to participants according to the risk assessment. All clinical procedures in this study (including COVID-related restrictions) will be carried out following a study-specific risk assessment and in adherence to the standard operating procedure of Neurosciences Building risk assessment (see APPENDIX C - NEUROSCIENCES BLDG RISK ASSESSMENT). If participants fit the study criteria they will then be invited for the second visit: 'Study visit'. A maximum of four weeks is allowed between the Screening Visit and the Study Visit. If this duration is exceeded, another screening will be performed to ensure eligibility.

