## **2. Subsequent Visits**

### Study Visit

Participants who are medically approved to take part in the study after the screening visit are invited to take part in the study visit. Prior to the study visit, and after the screening visit, participants will be randomised using the variance minimisation algorithm described above to ensure a balance of covariates of interest across treatment and placebo groups. The randomisation code will be drawn up by a researcher not involved in the study using an randomisation procedure known as variance minimisation, following a procedure outlined by Sella, Raz & Cohen Kadosh (2021). Participants will be allocated to placebo or treatment groups based on gender, level of education, and their digit span score (as an index of general intelligence). Allocation of treatments will be recorded on a Randomisation List which will be updated when each new participant enters the randomised phase. The Randomisation List will be held securely within the Neurosciences Building by the study medic ([name]). Pitolisant and placebo agents will be kept securely within a locked medicines cabinet also within the Neurosciences building.

During the visit, participants will receive either a single dose of pitolisant (36mg single dose) or placebo. They will receive the dose at the Neurosciences Building, Warneford Hospital site. The study has a double-blind design thus neither the researchers nor the participant will know whether pitolisant or placebo is given. On arrival, participants will briefly be reviewed to ensure the inclusion criteria are still satisfied. Prior to drug or placebo administration, the following procedures will be undertaken:

- Inclusion/exclusion criteria review

- Completion of the MRI screening form (APPENDIX H - 3T VOLUNTEER SCREENING FORM) once more to ensure it is still safe for them to undergo fMRI scanning.
- Clinical screening, mood and side effects questionnaires (to establish baseline) on qualtrics – PHQ-9, GAD-7, PANAS, PDQ and Need for Cognition Scale

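### Arms are balanced by minimisation on gender, education and digit span, but the stated ANOVA leaves these factors out, so it is conservative and loses power wherever they predict the outcome.

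*Protocol*

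**What the plan says.** - **Allocation (Section G.2, Study Visit).** "Participants will be allocated to placebo or treatment groups based on gender, level of education, and their digit span score". The stated purpose is "to ensure a balance of covariates of interest across treatment and placebo groups".
- **Digit span (Section G.1, Screening visit).** It is measured "to assess baseline cognitive ability for randomisation procedure". Section G.2 treats it as an index of general intelligence.
- **Outcome model (Section J.4).** "Cognitive and neuroimaging data will be analysed using a between-groups ANOVA approach, with appropriate normality transformations". The section adds Greenhouse–Geisser and Bonferroni corrections but names no covariate.
- **Where the factors reappear (Section J.4).** "Sample characteristic data (e.g. age, gender, and years in education) will be analysed using an appropriate analysis of variance". Gender and years in education occur only in this descriptive role. Digit span is not mentioned in the section.
- **Sample size (Section J.3).** It rests on a "one-way fixed effects ANOVA approach within a healthy volunteer population", with "Statistical power: 80%; Estimated effect size: 0.4; Alpha level: 0.05", giving 52 participants, raised to 56 (28 per group).

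No section of the protocol places a minimisation factor in an outcome model.

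**The concern.** The analysis should reflect the allocation. Minimisation makes the arms more alike on the chosen factors than chance would. If those factors predict the outcome, the difference between arms varies less from trial to trial than under simple randomisation. A model without the factors does not see this. It leaves their variation in the residual and reports a standard error that is too large.

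The result is a test that rejects too rarely under the null and has less power than the same data could give. Digit span is a baseline cognitive measure and several outcomes are working-memory tasks, so some prognostic value is plausible. It is less sure for the imaging, reward-learning and facial-emotion outcomes.

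The Greenhouse–Geisser wording implies within-person task factors in some models. This does not remove the point: the group main effect in such a model is the same test applied to each person's mean. For a group-by-condition effect, the point holds only as far as the factors predict the condition contrast.

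**Working it through.** **1. The protocol's own figure.** Inputs from Section J.3: effect size 0.4, read as Cohen's f (d = 0.8 for two equal groups), two-sided alpha 0.05, no covariates. Power comes from the noncentral F distribution with 1 and N − 2 degrees of freedom and noncentrality λ = N·f².

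- N = 50: λ = 50 × 0.16 = 8.00, power 79.1%
- N = 52: λ = 52 × 0.16 = 8.32, power 80.7%
- N = 56: λ = 56 × 0.16 = 8.96, power 83.6%

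So 52 is the smallest even total that reaches 80%, and the stated figure is reproduced.

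**2. Why the ANOVA standard error is too large.** Take a total outcome SD of 1 and 28 per arm. The ANOVA standard error is about √(2/28) = 0.267. If the factors explain R² of the variance and are perfectly balanced, the true standard error is √(1 − R²) × 0.267. At R² = 0.25 that is 0.866 × 0.267 = 0.231. Real minimisation falls a little short of perfect balance. Simulated at R² = 0.25, the ANOVA standard error is 0.267 against a true 0.246 with an 80:20 coin, and 0.268 against 0.233 with deterministic allocation.

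**3. Adjusted power by formula.** ANCOVA with three covariate degrees of freedom has N − 5 = 51 error degrees of freedom and λ = N·f²/(1 − R²). At N = 56:

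- R² = 0: λ = 8.96, power 83.6%
- R² = 0.10: λ = 8.96/0.90 = 9.96, power 87.2%
- R² = 0.25: λ = 8.96/0.75 = 11.95, power 92.4%
- R² = 0.40: λ = 8.96/0.60 = 14.93, power 96.6%

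**4. Simulation of both analyses under minimisation.** The settings were N = 56, d = 0.8, and one binary and two continuous factors with equal effects. Each person was assigned to reduce the summed absolute mean differences plus arm-size imbalance. There were 10,000 trials per setting (Monte Carlo error at most 0.5 points). R² is an assumed range. The protocol does not describe the random element of the allocation, so two rules are shown.

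| R² | Power unadjusted, 80:20 | Power adjusted, 80:20 | Gain, 80:20 | Type I error unadjusted, 80:20 | Gain, deterministic | Type I error unadjusted, deterministic |
|---|---|---|---|---|---|---|
| 0 | 83.0% | 82.2% | −0.8 | 5.1% | −0.4 | 4.7% |
| 0.10 | 84.4% | 86.8% | +2.4 | 4.5% | +2.4 | 3.8% |
| 0.25 | 85.1% | 92.2% | +7.1 | 3.2% | +6.1 | 2.5% |
| 0.40 | 87.2% | 96.4% | +9.2 | 2.2% | +7.7 | 1.6% |

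The adjusted type I error stays between 4.8% and 5.4%.

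**5. Sensitivity to the balancing rule.** A second simulation (4,000 trials per setting) used squared mean differences, with deterministic allocation and with a 20% random element. At R² = 0.3, unadjusted power was about 87% against 93–94% adjusted, and unadjusted type I error was 2.3–2.5%. With simple randomisation at R² = 0.3, power was 83.5% against 91.9% and unadjusted type I error was 4.3%. Most of the conservatism therefore comes from the balancing, but the power gain from adjustment does not depend on it.

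**The case against.** The best case against is that Section J.4 is a brief answer on an ethics form. It does not say that the analysis is unadjusted, and covariate lists are often left to a statistical analysis plan. A separate plan could add them. This does not remove the point: the protocol does more than stay silent, because it names a model, and that model does not match its own allocation. Sizing on a one-way ANOVA is compatible with a later adjusted analysis, so Section J.3 alone would not prove the mismatch.

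Several other objections stand as limits:

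- Nothing is biased, and unadjusted power exceeds 80% throughout the range shown.
- R² is unknown. At R² = 0 there is no gain and a loss of under 1 point. The gains of about 6 to 9 points need R² of 0.25 to 0.40, for which the protocol gives no support.
- The simulation assumes normal outcomes, equal factor effects and all 56 people analysed. Sections G.5 and I.3 exclude withdrawn and unblinded participants, which would loosen the balance. That would weaken the conservatism, but, as the simple-randomisation result shows, not the case for adjustment.
- No voxelwise imaging inference was computed.

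**Conclusion.** The concern holds. The protocol balances the arms on three factors and then states an outcome model that ignores them. To the extent that the factors predict an outcome, the group test runs below its nominal 5% level and gives up power. The loss is about 2 points at R² = 0.10, 6 to 7 at 0.25 and 8 to 9 at 0.40, depending on the allocation rule. If the factors predict nothing, nothing is lost.

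This is a matter of efficiency, not validity: estimates are unbiased, false positives are not inflated and the planned power is met. The figures rest on reading the effect size as f = 0.4, on the assumed R² range, and on a minimisation rule that the protocol gives only by citation. The change is worth making because possible gain and cost are so unequal.

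**What to change.** In Section J.4, replace the ANOVA sentence with wording such as:

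> Cognitive and neuroimaging outcomes will be analysed with a linear model (ANCOVA) of treatment group plus the minimisation factors gender, level of education (years) and digit span (continuous), keeping within-person task factors where a task has them. The same covariates will be entered in the FSL group-level design.

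State which digit span score is meant, since the task has forward and backward parts; it should be the one used for allocation. Years in education is the form that Sections I.3 and J.4 show is recorded. Fix the wording before unblinding, so that adjustment cannot be chosen after results are seen.

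The sample size calculation in Section J.3 can stay. The cost is analysis wording and 3 degrees of freedom (54 to 51 at N = 56), which is less than 1 point of power if the factors predict nothing. No further participants, visits or measurements are needed.
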